Appendix B- Location of accelerometry and actigraphy devices on the children participants Devices will be optional for child participants who have active AD on location of device placement, with a minimum of at least one wrist device needed for enrollment.

2 – ≤ 11 years old

3 months - < 2 years old

— Accelerometry

— Actigraphy or Accelerometry

Subject ID: _____

Date: _____

Technician Initials: _____

Lesion/Non-Lesion Tape Stripping Guide and Lesional/Non-Lesional Site Identification Form

Selection of lesional and non-lesional body location is as follows:

Lesional site: Identified at V01 based on BSA assessment (same site used throughout the study):

Lesional site anatomical location: _____
De-identified photo of lesional location captured: Y _____ N _____

Non-lesional site: Identified at V01 based on BSA assessment from skin that is unaffected by atopic dermatitis in a similar region of the body as the lesional site (opposite side of body is acceptable).

Non-lesional site anatomical location: _____
De-identified photo of non-lesional location captured: Y _____ N _____

Lesional tape strips will be collected from skin adjacent to an atopic dermatitis lesion that is part of the planned treatment area at the baseline (V01), Day 2 (V03), and the Day 15 (V05) visits. V03 and V05 lesional collections should be from the location as the V01 lesional collection, even if the severity of the lesion has changed.

Nonlesional tape strips will be collected from skin that is unaffected by atopic dermatitis at the baseline visit (V01) only. If possible, the nonlesional area where tape strips are collected should be in a similar region of the body (opposite side is okay) to where the lesional strips are collected and should be at least 2 cm from the selected lesion.

Mitigation of risk associated with tape stripping: Tape stripping will only be conducted three times during the study, with a minimum of 3 days between each tape stripping. If the participant ~~experiences~~ discomfort, adjacent sites to previous stripping area will be used, and this should be noted on the sample manifest.

Skin Tape Strip Collection Procedure:

1. Wearing gloves, apply a tape strip to the target area. Using a marker pen, make small marks on the skin after placement of the first tape strip to ensure consistent placement of subsequent tape strips at each site. Change to a fresh pair of gloves between non-lesional and lesional collections in order to avoid cross-contamination.
2. Apply pressure with the D-Squame pressure instrument for approximately three to five seconds. The pressure instrument has a plunger mechanism to ensure even/consistent pressure is applied to each tape strip.
3. As soon as the pressure is applied and released, the tape strips should be removed with gloved hands and stuck onto the D-Squame storage cards, as described above.
4. Cards with tape strips should be immediately stored on dry ice (or in a -20°C freezer) in the appropriate labeled specimen bag and then transferred to a -80°C freezer until shipment.

Samples collected and stored at site should be shipped approximately once every two weeks to Pfizer Clinical PGx Lab. Samples should be packaged using dry ice above and below the bags containing the frozen tape strips. Dry ice should be added to a Styrofoam shipping container and placed within a cardboard box. The shipping container should be at least $\frac{1}{2}$ to $\frac{3}{4}$ filled with dry ice to ensure that the specimens do not thaw during travel.

WORD READING SUBTEST

AGES 7 OR YOUNGER: Administer Part 1: Letter Reading first, followed by Part 2: Word Reading. Discontinue testing if a Participant has responded incorrectly to 10 consecutive items (*10 RULE*).

AGES 8 OR OLDER: Administer Part 2: Word Reading first. Discontinue the Word Reading section if the Participant has answered 10 consecutive items incorrectly (*10 RULE*). If the Participant has correctly answered 5 or more items on the Word Reading section before meeting the discontinue criterion, do not administer the preliminary Letter Reading section. If the Participant did not answer at least 5 items correctly on the Word Reading section, then administer Part 1: Letter Reading (*5 RULE*).

Part 1: Letter Reading Administration Instructions

After handing the Participant the Green Word Reading List, say, **I want you to look at the letters on this line.** (Point to the row of letters at the top of the card) **Read to me the letters one-by-one across the line.** After the Participant has finished, say, **That's all. Now let's do something different.**

A	B	O	S	E	R	T	H	U	P	I	V	Z	J	Q
(1)	(2)	(3)	(4)	(5)	(6)	(7)	(8)	(9)	(10)	(11)	(12)	(13)	(14)	(15)

Part 2: Word Reading Administration Instructions

After handing the Participant the Green Word Reading List, say, **Look at each of these words carefully.** (Point to the words) **Read the words across the page so I can hear you.** When you finish the first line, go right on to the second line, and so on down the page until you finish or I tell you to stop. Read slowly and say the words clearly. Allow 10 seconds for the Participant to respond to each word. If there is no response after 10 seconds, say, **OK, try the next one.** If you did not hear a word clearly, say, **I could not hear you clearly. Please say the word again just as you did the first time.** When the Participant has finished the Word Reading section, say, **That's all. Good job. Thanks. Now we are going to do something else.**

1. see	13. plot	25. rancid	37. novice	49. puerile
see	plot	ran-sid	nov-is	pyoo-e-rl̄
2. red	14. grunt	26. suspicion	38. longevity	50. internecline
red	grunt	sū-spish-ōn	lon-jev-i-tee	in-tēr-nee-seen, -nes-ccn
3. milk	15. sour	27. conspiracy	39. rescinded	51. ubiquitous
milk	sowr	kōn-spir-ā-see	ri-sind-ed	yoo-bik-wi-tūs
4. was	16. huge	28. deny	40. audacious	52. regicidal
wuz, woz	hyooj	di-n̄i	aw-day-shūs	rej-i-si-dāl
5. then	17. privilege	29. miscellaneous	41. extemporaneous	53. inefficacious
then	priv-i-līj	mis-ē-lay-ni-ūs	ik-stem-po-ray-ni-ūs	in-ef-i-kay-shūs
6. jar	18. license	30. quarantine	42. protuberance	54. epithalamion
jahr	li-sēns	kwōr-ā-teen	proh-too-bē-rāns	ep-i-thā-lay-mi-ōn
7. letter	19. humidity	31. deteriorate	43. diminutive	55. synecdoche
let-ēr	hyoo-mid-i-tee	di-teer-i-ō-rayt	di-min-yū-tiv	si-nek-dō-kee
8. city	20. gadget	32. concoct	44. factitious	
sit-ee	gaj-it	kōn-kōkt	fak-tish-ūs	
9. between	21. tough	33. coincide	45. regime	
bi-tween	tuf	ko-in-sid	rē-zheem	
10. cliff	22. residence	34. mosaic	46. predilection	
klif	rez-i-dēns	moh-zay-ik	pred-i-lek-shōn	
11. listen	23. urge	35. debris	47. lubrication	
lis-ēn	urj	dē-bree	loo-kyuu-bray-shōn	
12. wrap	24. clarify	36. rudimentary	48. sanguine	
rap	klar-i-fī	roo-di-men-ē-ree	sang-gwin	

Letter Reading Raw Score	/15
Word Reading Raw Score*	/55

Word Reading Total Raw Score	/70
------------------------------	-----

Next administer the Sentence Comprehension subtest, if applicable.
*Use this value for determining starting point on Sentence Comprehension subtest.

SPELLING SUBTEST

AGES 7 OR YOUNGER: Administer Part 1: Letter Writing first, followed by Part 2: Spelling. The Spelling section must be administered individually for participants ages 7 and younger. On the Spelling section, the test should be discontinued after the Participant spells 10 consecutive words incorrectly (*10 RULE*).

AGES 8 OR OLDER: Administer Part 2: Spelling first. Discontinue if 10 consecutive errors have been made (*10 RULE*). If the Participant has correctly spelled 5 or more items on the Spelling section before meeting the discontinue criterion, the preliminary Letter Writing section should not be administered. If the Participant does not spell at least 5 words correctly on the Spelling section, then administer Part 1: Letter Writing (*5 RULE*).

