layer of Crisaborole (2% BID) or vehicle twice daily (excluding mouth, eyes, and vagina, per label), to all locations with active lesions and record location and time of application on the daily dosing form (as identified on the Dosing Record Sheet, breastfeeding women will be instructed to use the provided gloves when applying crisaborole/vehicle). The study will be comprised of an initial screening/baseline visit for children participants who have an existing diagnosis of symptomatic AD, screened and enrolled in the study along with their primary caregivers after signing an informed consent (or parents/guardians and assent when appropriate). Upon enrollment child participants and caregiver participants will complete a one week acclimation and training phase, where the children will not be on medication, for wearing accelerometry/actigraphy and performing observer-reported outcome assessments (caregivers for participants) and self-reported outcome assessments (caregivers). After the one week acclimation and training phase, the child participants will be on a Crisaborole or vehicle treatment for two consecutive weeks. During those 2 weeks, the children, 3 months up to <2 years will wear one actigraphy or one accelerometry device on each wrist and one actigraphy or one accelerometry device on each ankle (optional for those who have active AD on location of device placement, with a minimum of at least one wrist device needed for enrollment). Children 2 years to \leq 11 years will wear one actigraphy or one accelerometry on each wrist (optional for those who have active AD on location of device placement, with a minimum of at least one wrist device needed for enrollment). The primary caregiver (parents/guardians) will also wear one accelerometer device on each wrist and complete daily assessments related to scratching, sleeping habits, pain, AD severity, quality of life, and device comfort questionnaires (parent/guardian will complete as appropriate). The participants will be asked to return to the laboratory on days 1, 2, 8, and 15 for assessments and biomarker assessment. At the completion of the study, Day 15 (\pm 3 day) participants (and primary caregiver) will return the devices, and will complete additional questionnaires. Participants may come in for an unscheduled visit as needed (i.e., to replace compound, etc.). During the performance of the study, participants will be monitored by the study dermatologist, and assess participant continuation throughout the study.

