Approximately 270 children, age 3 months to ≤ 11 years, and their primary caregiver as participants, for a total of 540 participants (270 pairs), will be randomized in 1:1 ratio to either Crisaborole (2% BID) or vehicle treatment and will be followed for 2 weeks, with an objective of approximately 50% of recruited child participants being ages 5 years old or younger. For this study, we will employ a simple randomization procedure. Participants will be randomly assigned (1:1) using computerized random numbers to receive either crisaborole or the vehicle. The participants will be asked to apply a thin even-layer of Crisaborole 2% or vehicle twice daily (excluding mouth, eyes, and vagina, per label), to all locations with active lesions and record location and time of application on the daily dosing form (as identified on the Dosing Record Sheet, breastfeeding women will be instructed to use the provided gloves when applying crisabrole/vehicle). The study will be comprised of an initial screening/baseline visit for children participants who have an existing diagnosis of symptomatic AD, screened and enrolled in the study along with their primary caregivers after signing an informed consent (or parents/guardians and assent when appropriate). Upon enrollment child participants and caregiver participants will complete a one week acclimation and training phase, where the children will not be on medication, for wearing accelerometry/actigraphy and performing observer-reported outcome assessments (caregivers for participants) and self-reported outcome assessments (caregivers). After the one week acclimation and training phase, the child participants will be on a Crisaborole or vehicle treatment for two consecutive weeks. During those 2 weeks, the children, 3 months up to <2 years will wear one actigraphy or one accelerometry device on each wrist and one actigraphy or one accelerometry device on each ankle (optional for those who have active AD on location of device placement, with a minimum of at least one wrist device needed for enrollment). Children 2 years to ≤ 11 years will wear one actigraphy or one accelerometry device on each wrist (optional for those who have active AD on location of device placement, with a minimum of at least one wrist device needed for enrollment). The primary caregiver (parents/guardians) will also wear one accelerometer device on each wrist and complete daily assessments related to scratching, sleeping habits, pain, AD severity, quality of life, and device comfort questionnaires (parent/guardian will complete as appropriate). The participants will be asked to return to the laboratory

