5. STUDY PROCEDURES

The study will consist of a screening/baseline (in- laboratory) visit on Day -7 (V01), an in- laboratory visit Day 1 (V02), an in- laboratory visit on Day 2 (V03) for tape-stripping, and Day 8 (V04) for an assessment of the severity of the AD and a final in- laboratory visit on Day 15 (V05) for an assessment of the AD, tape-stripping, completion of ObsROs and return devices. Throughout the study, the participants and caregivers will wear accelerometry/actigraphy devices continuously (optional for those who have active AD on location of device placement, with a minimum of at least one wrist device needed for enrollment; devices may be removed for short periods of time for such things as the purposes of bathing, etc.). Enrolled participants will be randomly assigned to each arm of the study. Participants may come in for an unscheduled visit as needed (i.e., to replace compound, etc.). All in-person study activities, including informed consent and pregnancy testing, will be completed at the Laboratory for Human Neurobiology, [name]. All activities performed in the laboratory are accomplished in private rooms. Primary caregivers will be provided with ample time and a privacy curtain to change into a gown during assessment for exclusion of Atopic Dermatitis, and primary caregivers will accompany children during all activities to ensure participant privacy. All at-home study activities will be completed in the participants' home.

Phone Screening - Day-28 to -7 (~15 minutes):

- Verbal consent (including assent where applicable)
- Assign Participant ID (a sequentially assigned numerical ID used to identify participant on all study documents and in the electronic data capture [EDC] system)
- Screening demographics, medical history including AD history/treatment (includes, race, ethnicity, and gender)
- Eligibility screening (review of inclusion and exclusion criteria)

Baseline Visit 1 (V01)/Day -7 (+/- 3) – In Laboratory (~2 hours):

- Written Informed consent (including assent when applicable)
- Participants are randomly assigned to one of the two arms of the study
- Screening demographics (includes race, ethnicity, gender, and significant medical

history/treatment)

- Pregnancy test for female caregivers of child-bearing potential
- Wide Range Achievement Test 4 (WRAT-4)
- Eligibility Screening (Inclusion/Exclusion criteria)
- Vital signs
- Height and weight

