1. ISGA
2. EASI
3. % affected BSA calculation
4. Children's Sleep Health Questionnaire (CSHQ; ages ≥ 4 to ≤ 11 years) OR BISQ (Brief Infant Sleep Questionnaire; ages 3 months - <4 years)
5. Medical Outcome Sleep Scale (MOS-Sleep; caregivers only)
6. Faces, Legs, Activity, Cry, and Consolability Scale (FLACC)
7. Dermatitis Family Impact Questionnaire (DFI; parent/guardian(s); ages 3 months - ≤ 11 years)
8. Children's Dermatology Life Quality Index (CDLQI; ages ≥ 4 - ≤ 11) OR Infants Dermatitis Quality Of Life Index (IDQOL; ages 3 months - <4 years)
9. Observer-Reported Patient-Oriented Eczema Measure (POEM; ages 3 months - ≤ 11 years)
10. In laboratory dose application training, including weight of the compound or vehicle tube
11. Drug Dispensing
12. Continuous accelerometry wear (Devices will be optional for child participants who have active AD on location of device placement, with a minimum of at least one wrist device needed for enrollment.)
13. Continuous actigraphy wear (Devices will be optional for child participants who have active AD on location of device placement, with a minimum of at least one wrist device needed for enrollment.)

Out-of-Laboratory (At-Home) Assessments (Days 1-15) (~15 minutes per day):

The purpose of the out-of-laboratory assessment is to evaluate wearable devices and ORIA/Patient Reported Itch Severity Scale in a home/routine setting (defined as the participant's routine environment/activities) while the child participant is receiving either crisabole or vehicle. Participants will be provided a fully-charged set of accelerometry devices for use at home.

1. Caregiver to complete ObsRO/PRO measurements as instructed:
 - Observer Reported Itch Assessment (ORIA; ages 3 months- ≤ 11 years)
 - Observer Global Impression of Severity (OGIS; ages 3 months- ≤ 11 years)
 - Peak Pruritis NRS (Caregivers)
 - Patient Reported Itch Severity Scale (Children 6- ≤ 11 years old)
2. At-home dosing (crisaborole or vehicle) in all affected areas except mouth, eyes, and vagina, per label
3. Continuous Accelerometry wear (Devices will be optional for child participants who have active AD on location of device placement, with a minimum of at least one wrist device needed for enrollment.)
4. Continuous Actigraphy wear (Devices will be optional for child participants who have active AD on location of device placement, with a minimum of at least one wrist device needed for enrollment.)

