11.4 Participant Recruitment and Participation

Recruitment: Advertisements, including via patient advocacy groups and pediatric dermatology clinics, approved by ethics committees and investigator databases may be used as recruitment procedures. Participants will be recruited via electronic announcements, the BUMC Corporate Communications weekly email, and posted flyers. Moreover, participants will be recruited through physician referral at the dermatology clinics. BuildClinical, a recruitment platform, will also be used to identify potential study participants, in accordance with BUMC policy. Individuals who respond to recruitment materials will be provided with a brief description of the study, including the methodologies used, and asked a series of questions to determine eligibility and informed that snacks and liquids will be available during onsite study visits. The investigators will maintain a list containing the names and contact information (but absolutely no protected health information) of those individuals who are ineligible.

Location where study will be performed: Boston University

Participant payment:

Participants who partially complete study activities will be compensated based on activities completed, outlined below. Participants whose total amount of compensation for activities completed is less than \$400 will be paid through Cash Cards. Participants whose total amount of compensation for activities completed is greater than \$400 will be paid via checks after study withdrawal or completion. Participant Compensation (inclusive of child and caregiver; all study activities): \$1,350

- V01 [Day -7] (Intake): \$25
- V01 [Day -7] (Baseline: completion of PROs, training, tape stripping, assessments): \$150
- V02 [Day 1] (Completion of PROs / assessments): \$100
- V03 [Day 2]: (Tape stripping): \$200
- V04 [Day 8]: Completion of PROs / assessments): \$100
- In-Home Activities [Day -7 to Day 15]: \$525
- V05 [Day 15]: (In-lab assessments, turn-in wearable devices): \$250

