IDQOL
SCORE

The aim of this chart is to record how your child's dermatitis has been. Each question concerns THE LAST WEEK ONLY. Please could you answer every question.

Dermatitis Severity

Over the last week, **how severe** do you think your child's dermatitis has been?, i.e. how red, scaly, inflamed or widespread.

Extremely severe
Severe
Average
Fairly good
None

Life Quality Index

1. Over the last week, how much has your child been **itching and scratching**?

All the time
A lot
A little
None

2. Over the last week, what has your child's **mood** been?

Always crying, extremely difficult
Very fretful
Slightly fretful
Happy

3. Over the last week approximately how much **time** on average has it taken **to get your child off to sleep** each night?

More than 2 hrs
1 - 2 hrs
15mins - 1 hr
0-15mins

4. Over the last week, what was the **total time** that your child's **sleep was disturbed** on average each night?

5 hrs or more
3 - 4 hrs
1 - 2 hrs
Less than 1 hour

5. Over the last week, has your child's eczema interfered with **playing or swimming**?

Very much
A lot
A little
Not at all

6. Over the last week, has your child's eczema interfered with your child **taking part in or enjoying other family activities**?

Very much
A lot
A little
Not at all

7. Over the last week, have there been problems with your child at **mealtimes** because of the eczema?

Very much
A lot
A little
None

8. Over the last week, have there been problems with your child caused by the **treatment**?

Very much
A lot
A little
None

9. Over the last week, has your child's eczema meant that **dressing and undressing** the child has been **uncomfortable**?

Very much
A lot
A little
None

10. Over the last week how much has your child having eczema been a problem at **bathtime**?

Very much
A lot
A little
None

Please can you check that you have answered every question.

© M.S. Lewis-Jones, A.Y. Finlay Jan 2000

Subject ID: _____

Date: _____

Technician Initials: _____

OBSERVER REPORTED GLOBAL IMPRESSION OF CHANGE (OGIC)

Place an X in the box you feel most closely describes any change which the child has experienced. Take into account all change, whether or not you believe it is entirely due to drug treatment.

Select only ONE response.

Since the start of the study, the child's atopic dermatitis is:

Very much improved	
Much improved	
Minimally improved	
No change	

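### The OGIC asks about change since an undefined study start, most naturally Day -7, so its Day 8 and Day 15 categories cannot be read as change on treatment

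*Combined protocol and SAP*

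**What the plan says.** Section 2 lists the OGIC among the secondary disease-severity endpoints, and Section 9 tests secondary endpoints at a two-sided 0.05 level. The form in Appendix C has seven categories under the stem "Since the start of the study, the child's atopic dermatitis is". Its instruction to the caregiver is "Take into account all change, whether or not you believe it is entirely due to drug treatment". It prints no date and does not mention the first application.

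The calendar comes from elsewhere in the protocol:

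- Section 5 opens with "The study will consist of a screening/baseline (in- laboratory) visit on Day -7 (V01), an in- laboratory visit Day 1 (V02" and places written consent, randomisation, baseline assessments and device issue at V01.
- Section 3 describes the first week: "Upon enrollment child participants and caregiver participants will complete a one week acclimation and training phase, where the children will not be on medication". After it, "the child participants will be on a Crisaborole or vehicle treatment for two consecutive weeks".
- Ointment is handed out at V02; the visit list in Section 5 has "11. Drug Dispensing".
- The payment list in Section 11.4 has "In-Home Activities [Day -7 to Day 15", so home participation is counted from Day -7.
- The Schedule of Activities and the visit lists in Section 5 collect the OGIC at V04 (Day 8) and V05 (Day 15) only.

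**The concern.** A global impression of change compares the child now with the child at a remembered earlier point. If that point is Day -7, the rating covers an untreated week as well as the treated days. A child who worsened in that week and then recovered on ointment could be rated as unchanged. A child who improved before the first dose could be rated as improved.

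The stated goal of the study (Section 3) is early relief once treatment begins, so the category labels would not answer the question a reader brings to them.

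The undefined anchor adds a second problem. Section 5 has a phone screening with verbal consent between Day -28 and Day -7, then V01, then the first ointment at V02. A caregiver could reasonably take any of these as the start, so different families may rate different intervals on the same scale.

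**Working it through.** **Plan's own figure.** The documents give no precision or power figure for the OGIC. The only one, in Section 9, is about 85% power for the itch score with 244 children, a difference of 1.0 and an SD of 2.6 at two-sided 5%. With 122 per arm, 1.0 / (2.6 × √(2/122)) = 3.004, and Φ(3.004 − 1.960) = 0.852, so it reproduces. It serves below only as a benchmark.

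**Untreated share on nominal days.** Inputs: 7 untreated days (V01 to V02, the one-week phase of Section 3), and 7 treated days at Day 8 or 14 at Day 15, assuming first application on Day 1. Share = untreated / (untreated + treated).

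- Day 8: 7 / (7 + 7) = 7/14 = 50%.
- Day 15: 7 / (7 + 14) = 7/21 = 33%.
- If a Day 0 is counted: 8/15 = 53% and 8/22 = 36%.

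**Other readings of the start.** Anchored to the first application, the share is 0% at both visits and the rated intervals are 7 and 14 days. Anchored to a phone screening as early as Day -28, the time before ointment is 28/35 = 80% at Day 8 and 28/42 = 67% at Day 15.

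**Visit windows.** V01 and V02 each carry ±3 days.

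- Shortest untreated stretch: 7 − 3 − 3 = 1 day. Longest: 7 + 3 + 3 = 13 days. With a Day 0 counted, these become 2 and 14.
- Letting V04 and V05 also move by ±3 days, the share at Day 8 runs from 1/(1 + 13) = 7% to 13/(13 + 1) = 93%. At Day 15 it runs from 1/(1 + 20) = 5% to 13/(13 + 8) = 62%.
- These are extremes, with every visit at the edge of its window. They are not expected values.

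**Can it be corrected afterwards?** EASI, ISGA, BSA and POEM are measured at both V01 and V02, so change from just before treatment can be computed for them. The OGIC has no V02 rating and no baseline value, so the baseline covariate in the Section 9 models cannot take out the untreated week.

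**Noise, as an illustration only.** The documents give no variance for this. Assume that the OGIC behaves like a difference between two severities and that weekly severities follow an AR(1) correlation ρ. The SD of change from Day -7, relative to change from Day 1, is then √((1 − ρ²)/(1 − ρ)) at Day 8 and √((1 − ρ³)/(1 − ρ²)) at Day 15. The last two columns show what happens to a comparison that would otherwise have 85% power.

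| ρ | SD ratio, Day 8 | SD ratio, Day 15 | Power, Day 8 | Power, Day 15 |
|---|---|---|---|---|
| 0 | 1.00 | 1.00 | 85% | 85% |
| 0.3 | 1.14 | 1.03 | 75% | 83% |
| 0.9 | 1.38 | 1.19 | 59% | 71% |

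If the correlation is constant over time, nothing is lost. The result depends wholly on the assumed structure, so no single figure should be taken from it.

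**The case against.** The sponsor has several fair replies.

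- **The anchor follows the plan.** The Schedule of Activities labels V01 as baseline, and the specific analyses in Section 9 compare study start with on-treatment values, including the observer-reported measures. This shows that the wording may be deliberate. It does not turn the rating into a measure of change on treatment, and it leaves the form undefined for the caregiver. Nor is it the only reference in Section 9: the primary model takes ORIA from Day 2, which suggests, without saying so, a baseline just before dosing.
- **There is no bias.** This stands. Children are randomised at V01 and both arms spend the same week untreated. A reader might infer that the treatment comparison is distorted, but the documents do not support that.
- **The percentages are not harm.** This also stands. A reader might infer that a third to a half of the treatment signal is lost. The OGIC compares two points and does not average over the interval, so a share of time says nothing direct about the effect.
- **Worsening in the untreated week is hypothetical.** Correct. Exclusion criterion 3 already requires 7 days off topical treatment before V01, and nothing shows a systematic shift between V01 and V02. What remains is possible fluctuation in either direction.
- **Change on treatment is captured elsewhere.** OGIS is rated daily from Day 1, and EASI, ISGA and POEM are taken at V02. This limits the damage to the trial but does not repair the OGIC.

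**Conclusion.** The point holds as one of wording and interpretation. The OGIC stem leaves its reference undefined. On the most natural reading, 50% of the rated interval at Day 8 and 33% at Day 15 fall before any ointment, with an untreated stretch of 1 to 13 days across the visit windows. The categories therefore cannot be reported as change on treatment, the ratings may carry pre-treatment fluctuation, and the data offer no direct correction.

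This rests on two assumptions: that caregivers take V01 as the start, which the form does not state, and that the first application is on Day 1. If a caregiver takes the start to be the first application, the untreated share is zero. That uncertainty is itself part of the fault. The size of any added noise cannot be derived from the documents.

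The OGIC is one of many secondary endpoints and does not drive the sample size. The change is a cheap improvement; nothing here puts the primary comparison in doubt.

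**What to change.** On the Day 8 and Day 15 forms, replace the opening words of the stem with *Since starting the study ointment* and leave the rest of the item as it is. The untreated share becomes 0% at both visits, and the rated intervals become 7 and 14 days on nominal days. No visit, procedure or treatment is affected.

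The cost is a one-line form amendment. Section 11.2 requires prospective IRB approval, so notification alone is not enough. Ratings already collected under the present stem should be flagged and reported separately, so that two stems are not mixed within one endpoint.

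If the wording must stay, define the start of the study on the form and in Section 9, and label the OGIC results as change since that date.
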